8.1.1 Trial Overview

A trial overview is described below. The trial flowcharts are shown in Table 1 and Table 2 for the Dose Escalation part and Table 3 and Table 4 for the Cohort Expansion part according to the initially designed treatment scheme. The trial flowchart for the Cohort Expansion part after implementation of the urgent safety measure (Protocol Amendment 4.0) is shown in Table 5 and Table 6. Trial evaluations by visit are detailed in Section 9.

Table 1: Trial Flow Chart-Dose Escalation Part

Treatment Cycle	Screening				Cycle 1	1				Cycl	e 2-4			Cycle	5-12 ¹		Follow - up	EOT ²	Withd- rawal Safety Follow- up ³	Unsche- duled
Visit Number	0	1^{4}	2	3^{4}	4^{4}	5	6	7	1^{4}	2^4	3^4	4	1^{4}	2^4	3^4	4	1-4	-	-	1-X
Day/Week	≤21 days prior to Visit C1-V1	1d	2d	8d	15d	16d	18d	22d	1d	8d	15d	22d	1d	8d	15d	22d	6 weekly	-	30 days after last dosing	-
Visit window ⁵		-	-	±1d	±1d	+1d	±1d	±1d	±3d	±1d	±1d	±1d	±3d	±1d	±1d	±1 d	±7d	-	±14d	-
Informed Consent	X^6																			
Eligibility Criteria	X																			
Demographics	X																			
Medical History ⁷	X																			
Height and Body Weight ⁸	X	X							X				X					X		
Physical Examination	X	X																X		
Vital Signs ⁹	X	X	X	X	X	X	X	X	X	X	X	X	X	X	X	X		X		X^{10}
ECG ¹¹	X	X							X				X					X		X^{10}
CT-Scan	X^{12}								X^{13}				X^{13}				X	X^{13}		X^{10}
ECOG Performance Status	X	X							X				X					X		X^{10}
Adverse Events	X	X	X	X	X	X	X	X	X	X	X	X	X	X	X	X	X	X	X	X^{10}
Concomitant Medication	X	X	X	X	X	X	X	X	X	X	X	X	X	X	X	X	X	X		X^{10}
Trial Drug Administration		X		X	X				X	X	X		X	X	X					
Bleeding Assessment	X	X	X	X	X	X	X	X	X	X	X		X	X	X			X		

Treatment Cycle	Screening				Cycle 1	1				-	e 2-4			Cycle	5-121		Follow - up	EOT ²	Withd- rawal Safety Follow- up ³	Unsche- duled
Visit Number	0	1^4	2	3^{4}	44	5	6	7	1^4	2^4	3^4	4	1^{4}	2^4	3^4	4	1-4	-	-	1-X
Day/Week	≤ 21 days prior to Visit C1-V1	1d	2d	8d	15d	16d	18d	22d	1d	8d	15d	22d	1d	8d	15d	22d	6 weekly	-	30 days after last dosing	-
Visit window ⁵		-	-	±1d	±1d	+1d	±1d	±1d	±3d	±1d	±1d	±1d	±3d	±1d	±1d	±1 d	±7d	-	±14d	-
Skin Assessment	X	X	X	X	X	X	X	X	X	X	X		X	X	X		X	X		X^{10}
Neuropathy Assessment	X	X		X	X			X	X	X	X	X	X	X	X	X	X	X		X^{10}
Ophthalmological Evaluation	X							X ²²				X^{22}				X^{22}		X^{22}		$X^{10,22}$
Radionuclide Bone Scan ¹⁴	X												X							X^{10}
LABORATORY AS	SSESSMENT	Γ S 15																		
Hematology	X	X	X	X	X	X	X	X	X	X	X	X	X	X	X	X	X	X		X^{10}
Biochemistry	X	X	X	X	X	X	X	X	X	X	Χ	X	X	X	X	X	X	X		X^{10}
Coagulation factors	X	X	X	X	X	X	X	X	X	X	X	X	X	X	X	X	X	X		X^{10}
PSA ¹⁴	X	X							X				X				X	X		X^{10}
CA 125 ¹⁶	X^{16}	Χ							X				X				X	X		X^{10}
Flow Cytometry		X^{17}											X^{17}					X		X^{10}
Pregnancy Test	X	X							X				X				X	X		X^{10}
ADA (Immunogenicity)	X	X							X				X				X			X^{10}
Hepatitis B, C, CMV, HPV ¹⁸	X																	X		X^{10}
PK Sampling ¹⁹	X	Χ	X	X	X	X	X	X	X	X	Χ		X	X	X					X^{10}
Tumor biopsy	X^{21}																			X^{10}

Treatment Cycle	Screening				Cycle 1	1				Cycl	le 2-4			Cycle	5-121		Follow - up	EOT ²	Withd- rawal Safety Follow- up ³	Unsche- duled
Visit Number	0	1^{4}	2	3^4	44	5	6	7	1^{4}	2^4	3^{4}	4	1^{4}	2^4	3^4	4	1-4	-	-	1-X
Day/Week	≤ 21 days prior to Visit C1-V1	1d	2d	8d	15d	16d	18d	22d	1d	8d	15d	22d	1d	8d	15d	22d	6 weekly	-	30 days after last dosing	-
Visit window ⁵		-	-	±1d	±1d	+1d	±1d	±1d	±3d	±1d	±1d	±1d	±3d	±1d	±1d	±1 d	±7d	-	±14d	-
Biomarkers	X	-									•	•	X^{21}							

Abbreviations: ADA=anti-drug antibody; CMV=cytomegalovirus; CRPC=Castration-resistant prostate cancer; CT=computerized tomography; ECG=electrocardiogram; ECOG=Eastern Cooperative Oncology Group; EOT=End of Trial; HBc=Hepatitis B core; HBs=Hepatitis B surface; HBsAg=Hepatitis B surface antigen; HCV=hepatitis C virus; HPV= human papilloma virus; Ig=Immunoglobulin; PCR=polymerase chain reaction; PD=progressive disease; PK=pharmacokinetic; PSA=prostate specific antigen; SAE=serious adverse event

Footnotes to Trial Flowchart: Dose Escalation Part

- ¹ Additional treatment only if patient shows response of SD or better.
- ² If the patient shows PD, is to start new anti-cancer treatment or withdraws from trial due to another reason during treatment or Follow-up period, the EOT Visit should be performed as soon as possible after decision of withdrawal. If patient completes all Follow-up visits, the EOT Visit should be performed 4 weeks after end of Follow-up Visit 4 period.
- ³ For patients who withdraw from the trial before Follow-Up Visit 1. Only SAEs will be assessed.
- ⁴ The patient shall stay at hospital for at least 2 hours after the infusion and may be requested to stay longer at the discretion of the investigator.
- ⁵ The specified visit windows are in accordance with the previous visit. Visit 1 of Cycle 2 and onwards should be performed 7 days ± 3 days after Day 22 of the previous cycle.
- ⁶ Informed consent must be obtained before or at the Screening Visit window i.e., may be reasonably prior to the screening date.
- ⁷ Signs and symptoms occurring between Visit 0 and first infusion should be recorded as medical history (see Section 10.2 for details). SAEs should be reported as of the signing of the informed consent.
- ⁸ Height is only assessed at the Screening Visit. During the trial, only body weight is measured on the first dosing day in a cycle, as part of the dose calculation. If body weight is assessed ≤ 7 days before the first day of the planned dosing in a cycle, this value can be used to calculate dose.
- ⁹ Temperature, blood pressure and heart rate. Within each visit, preferably the same equipment shall be used for vital signs measurements. Vital signs should be assessed just before and no longer than 30 minutes before infusion start, during and after the infusions until 2 hours after end of infusions, as indicated in Section 10.5.
- ¹⁰ Optional.
- ¹¹ One ECG will be performed at screening. Three ECGs should be performed at least 2 minutes apart before infusion of the trial drug on Visit 1 for all cycles, in accordance with the ECG Specifications Manual.

Footnotes to Trial Flowchart: Dose Escalation Part

¹² Within 4 weeks prior to Visit C1-V1. All patients will have a CT-scan with contrast of thorax, abdomen and pelvis performed as part of the screening procedure. If a CT-scan has been performed within 4 weeks prior to Visit C1-V1 as part of standard procedure, it is acceptable as screening CT-scan for the trial. If there is suggestion of brain metastases/tumors, a CT-scan of the head will be performed before inclusion.

¹³ At the end of every second cycle, i.e., on Day 1 of Cycles 3, 5, 7, 9 and 11, CT-scans can be performed up to 7 days before Day 1 of the relevant cycle to ensure result to be available before subsequent dosing. Additional scans on 21 days (± 7 days) after Day 15 of Cycle 12, and at the EOT Visit. To be completed as indicated to confirm response, new symptoms, end of trial or physician discretion.

¹⁴ Radionuclide bone scan and PSA will be performed for CRPC patients. Radionuclide bone scan will be performed at screening, every 16 weeks (i.e., Day 1 of Cycles 5 and 9), and upon clinical indication. If there is suspicion of progression, another bone scan will be performed 12 weeks later. The screening radionuclide bone scan can be performed up to 4 weeks prior to Visit C1-V1.

15 Hematology, biochemistry, serology and pregnancy test will be analyzed locally at the sites. All other laboratory parameters will be analyzed centrally.

¹⁶ For patients with ovarian and endometrial cancer. In patients with ovarian cancer, the screening sample should be taken within two weeks before starting the treatment.

¹⁷ Flow cytometry only on Cycle 1 and Cycle 5.

¹⁸ HBsAg, anti-HBs and anti-HBc, Hepatitis C and antibodies to CMV antigen will be assessed at screening for all patients; for CMV, anti-IgG and IgM will be assessed and, in case of positive IgM, it will be confirmed with CMV PCR; for HCV, anti-IgG will be assessed and, if positive, it will be confirmed with HCV PCR. HPV only for patients with cervical cancer. At EOT, only antibodies to CMV antigen will be assessed.

¹⁹ See Table 2 and Section 10.17or details of PK samplings.

²⁰ Archived biopsy material can be forwarded if a sample is available. If no sample is available, a new tumor biopsy must be obtained at least 2 weeks before dosing to ensure healing of wound.

²¹ Only on Cycle 5.

²² Patients experiencing ocular symptoms must be referred to an ophthalmologist for prompt review (preferably within 72 hours and no later than within one week).

Table 2: PK Sampling- Dose Escalation Part

Treatment Cycle	Screening				Cycle 1	-				Cycl	le 2-4			Cycle	5-12		Unscheduled
Visit Number	0	1	2	3	4	5	6	7	1	2	3	4	1	2	3	4	1-X
Day/Week	-	1d	2d	8d	15d	16d	18d	22d	1d	8d	15d	22d	1d	8d	15d	22d	
Before Infusion (on infusion days)	X	X	X	X	X	X	X	X	X	X	X		X	X	X		X2
End of infusion (+15 minutes) ¹		X		X	X				X	X	X		X	X	X		
+ 2 hours (± 15 minutes) after end of infusion ¹		X		X	X												

¹ Allowed time windows are indicated in parentheses.

² Optional.

 Table 3:
 Trial Flow Chart – Cohort Expansion Part - SUPERSEDED

Treatment Cycle	Screening			Cycle 1				Cyc	le 2-9		EOT ¹	Withdrawal Safety Follow-up ²	Unscheduled
Visit Number	0	1^3	2^3	3^3	4	5	1^3	2 ³	3^3	4	-	-	1-X
Day/Week	≤ 21 days prior to Visit C1-V1	1d	8d	15d	18d	22d	1d	8d	15d	22d	-	30 days after last dosing	-
Visit window ⁴		-	±1d	±1d	-±1d	±1d	±3d	±1d	±1d	±1d	-	±14d	-
Informed Consent	X^5												
Eligibility Criteria	X												
Demographics	X												
Medical History ⁶	X												
Height and Body Weight ⁷	X	X					X				X		
Physical Examination	X	X									X		
Vital Signs ⁸	X	X	X	X	X	X	X	X	X	X	X		X^9
ECG ¹⁰	X	X					X				X		X^9
CT-Scan	X^{11}						X^{12}				X^{12}		X^9
ECOG Performance Status	X	X					X				X		X^9
Adverse Events	X	X	X	X	X	X	X	X	X	X	X	X	X^9
Concomitant Medication	X	X	X	X	X	X	X	X	X	X	X		X^9
Trial Drug Administration ²²		X	X	X			X	X	X				
Bleeding Assessment	X	X				X	X				X		X
Skin Assessment	X	X				X	X				X		X
Neuropathy Assessment	X	X				X	X				X		X
Ophthalmological Evaluation	X					X^{13}				X^{13}	X^{13}		X^{13}
Radionuclide Bone Scan ¹⁴	X						X						X^9
LABORATORY ASSESSME	CNTS ¹⁵												
Hematology	X	X	X	X	X	X	X	X	X	X	X		X^9
Biochemistry	X	X	X	X	X	X	X	X	X	X	X		X^9
Coagulation factors	X	X	X	X	X	X	X	X	X	X	X		X^9

Treatment Cycle	Screening			Cycle 1				Cycl	le 2-9		EOT ¹	Withdrawal Safety Follow-up ²	Unscheduled
Visit Number	0	1^3	2 ³	3^3	4	5	1^3	2 ³	3^3	4	-	-	1-X
Day/Week	≤ 21 days prior to Visit C1-V1	1d	8d	15d	18d	22d	1d	8d	15d	22d	-	30 days after last dosing	-
Visit window ⁴		-	±1d	±1d	-±1d	±1d	±3d	±1d	±1d	±1d	-	±14d	-
PSA ¹⁴	X	X					X				X		X^{10}
CA 125 ¹⁶	X	X					X				X		X^{10}
Flow Cytometry		X^{17}					X^{17}				X		X^{10}
Pregnancy Test	X	X					X				X		X^{10}
ADA (Immunogenicity)	X	X					X						X^{10}
Hepatitis B, C, CMV, HPV ¹⁸	X										X		X^{10}
PK Sampling ¹⁹	X	X	X	X	X	X	X	X	X				X^{10}
Tumor biopsy	X^{20}					·							X^{10}
Biomarker	X					·			X^{21}				

Abbreviations: ADA=anti-drug antibody; CMV=cytomegalovirus; CRPC=Castration-resistant prostate cancer; CT=computerized tomography; ECG=electrocardiogram; ECOG=Eastern Cooperative Oncology Group; EOT=End of Trial; HBc=Hepatitis B core; HBs=Hepatitis B surface; HBsAg=Hepatitis B surface antigen; HCV=hepatitis C virus; HPV= human papilloma virus; Ig=Immunoglobulin; PCR=polymerase chain reaction; PD=progressive disease; PK=pharmacokinetic; PSA=prostate specific antigen; SAE=serious adverse event

Footnotes to Trial Flowchart: Cohort Expansion Part

¹ If the patient shows PD, is to start new anti-cancer treatment or withdraws from trial due to another reason during treatment, the EOT Visit should be performed as soon as possible after decision of withdrawal.

² Only SAEs will be assessed.

³ The patient shall stay at hospital for at least 2 hours after the infusion and may be requested to stay longer at the discretion of the investigator.

⁴ The specified visit windows are in accordance with the previous visit. Visit 1 of Cycle 2 and onwards should be performed 7 days ± 3 days after Day 22 of the previous cycle.

⁵ Informed consent must be obtained before or at the Screening Visit window i.e., may be reasonably prior to the screening date.

⁶ Signs and symptoms occurring between Visit 0 and first infusion should be recorded as medical history (see Section 10 for details). SAEs should be reported as of the signing of the informed consent.

 $^{^{7}}$ Height is only assessed at the Screening Visit. During the trial, only body weight is measured on the first dosing day in a cycle, as part of the dose calculation. If body weight is assessed ≤ 7 days before the first day of the planned dosing in a cycle, this value can be used to calculate dose.

⁸ Temperature, blood pressure and heart rate. Within each visit, preferably the same equipment shall be used for vital signs measurements. Vital signs should be assessed just before and no longer than 30 minutes before infusion start, during and after the infusions until 2 hours after end of infusions, as indicated in Section 10.5.

⁹ Optional

Footnotes to Trial Flowchart: Cohort Expansion Part

¹⁰ One ECG will be performed at screening. Three ECGs should be performed at least 2 minutes apart before infusion of the trial drug on Visit 1 for all cycles, in accordance with the ECG Specifications Manual.

¹¹ Within 4 weeks prior to Visit C1-V1. All patients will have a CT-scan with contrast of thorax, abdomen and pelvis performed as part of the screening procedure. If a CT-scan has been performed within 4 weeks prior to Visit C1-V1 as part of standard procedure, it is acceptable as screening CT-scan for the trial. If there is suggestion of brain metastases/tumors, a CT-scan of the head will be performed before inclusion.

¹² At the end of every second cycle, i.e., on Day 1 of Cycles 3, 5, 7 and 9, CT-scans can be performed up to 7 days before Day 1 of the relevant cycle to ensure result to be available before subsequent dosing. Additional scan at the EOT Visit. To be completed as indicated to confirm response, new symptoms, end of trial or physician discretion.

¹³ Patients experiencing ocular symptoms must be referred to an ophthalmologist for prompt review (preferably within 72 hours and no later than within one week).

¹⁴ Radionuclide bone scan and PSA will be performed for CRPC patients. Radionuclide bone scan will be performed at screening, every 16 weeks (i.e., Day 1 of Cycles 5 and 9), and upon clinical indication. If there is suspicion of progression, another bone scan will be performed 12 weeks later. The screening radionuclide bone scan can be performed up to 4 weeks prior to Visit C1-V1.

¹⁵ Laboratory parameters will be analyzed centrally.

¹⁶ For patients with ovarian and endometrial cancer.

¹⁷ Flow cytometry only on Cycle 1 and Cycle 5.

¹⁸ HBsAg, anti-HBs and anti-HBc, Hepatitis C and antibodies to CMV antigen will be assessed at screening for all patients; for CMV, anti-IgG and IgM will be assessed and, in case of positive IgM, it will be confirmed with CMV PCR; for HCV, anti-IgG will be assessed and, if positive, it will be confirmed with HCV PCR. HPV only for patients with cervical cancer. At EOT, only antibodies to CMV antigen will be assessed.

¹⁹ See Table 4 and Section 10.17 for details of PK samplings.

²⁰ Archived biopsy material can be forwarded if a sample is available. If no sample is available, a new tumor biopsy must be obtained at least 2 weeks before dosing to ensure healing of wound.

²¹ Only on Cycle 4.

²² Preventive eye therapy to be administered in relation to infusions as detailed in Section 8.4.5.3.

Table 4: PK Sampling - Cohort Expansion Part - SUPERSEDED

Treatment Cycle	Screening			Cycle 1				Cycle 2-9		Unscheduled
Visit Number	0	1	2	3	4	5	1	2	3	1-X
Day/Week	-	1d	8d	15d	18d	22d	1d	8d	15d	
Before Infusion (on infusion days)	X	X	X	X	X	X	X	X	X	X^2
End of infusion (+15 minutes) ¹		X					X			
+ 2 hours (± 15 minutes) after end of infusion ¹		X								

¹ Allowed time windows are indicated in parentheses.

² Optional.

 Table 5:
 Trial Flow Chart – Cohort Expansion Part - After Urgent Safety Measure

Treatment Cycle	Screening		Cycle 1			Cycle 2-9	1	EOT ¹	Withdrawal Safety Follow-up ²	Unscheduled
Visit Number	0	13	2	3	1 ³	2	3	-	-	1-X
Day/Week	≤ 21 days prior to Visit C1-V1	1d	8d	15d	1d	8d	15d	-	30 days after last dosing	-
Visit window ⁴		-	±1d	±1d	±3d	±1d	±1d	-	±14d	-
Informed Consent	X ⁵									
Eligibility Criteria	X									
Demographics	X									
Medical History ⁶	X									
Height and Body Weight ⁷	X	X			X			X		
Physical Examination	X	X						X		
Vital Signs ⁸	X	X	X	X	X		X	X		X^9
ECG ¹⁰	X	X			X			X		X^9
CT-Scan	X ¹¹				X^{12}			X^{12}		X^9
ECOG Performance Status	X	X			X			X		X ⁹
Adverse Events	X	X	X	X	X		X	X	X	X ⁹
Concomitant Medication	X	X	X	X	X		X	X		X^9
Trial Drug Administration ²²		X			X					
Bleeding Assessment	X	X		X	X			X		X
Skin Assessment	X	X		X	X			X		X
Neuropathy Assessment	X	X		X	X			X		X
Ophthalmological Evaluation	X			X^{13}			X^{13}	X ¹³		X^{13}
Radionuclide Bone Scan ¹⁴	X				X					X^9
LABORATORY ASSESSMENT	Γ S ¹⁵									
Hematology	X	X	X	X	X	X	X	X		X^9
Biochemistry	X	X	X	X	X	X	X	X		X^9
Coagulation factors	X	X	X	X	X	X	X	X		X^9

Treatment Cycle	Screening		Cycle 1			Cycle 2-9		EOT ¹	Withdrawal Safety Follow-up ²	Unscheduled
Visit Number	0	1^3	2	3	13	2	3	-	-	1-X
Day/Week	≤21 days prior to Visit C1-V1	1d	8d	15d	1d	8d	15d	-	30 days after last dosing	-
Visit window ⁴		-	±1d	±1d	±3d	±1d	±1d	-	±14d	-
PSA ¹⁴	X	X			X			X		X^{10}
CA 125 ¹⁶	X	X			X			X		X ¹⁰
Flow Cytometry		X^{17}			X ¹⁷			X		X^{10}
Pregnancy Test	X	X			X			X		X^{10}
ADA (Immunogenicity)	X	X			X					X^{10}
Hepatitis B, C, CMV, HPV ¹⁸	X							X		X^{10}
PK Sampling ¹⁹	X	X	X	X	X	X	X			X^{10}
Tumor biopsy	X^{20}									X^{10}
Biomarker	X						X^{21}			

Abbreviations: ADA=anti-drug antibody; CMV=cytomegalovirus; CRPC=Castration-resistant prostate cancer; CT=computerized tomography; ECG=electrocardiogram; ECOG=Eastern Cooperative Oncology Group; EOT=End of Trial; HBc=Hepatitis B core; HBs=Hepatitis B surface; HBsAg=Hepatitis B surface antigen; HCV=hepatitis C virus; HPV= human papilloma virus; Ig=Immunoglobulin; PCR=polymerase chain reaction; PD=progressive disease; PK=pharmacokinetic; PSA=prostate specific antigen; SAE=serious adverse event

Footnotes to Trial Flowchart: Cohort Expansion Part

¹ If the patient shows PD, is to start new anti-cancer treatment or withdraws from trial due to another reason during treatment, the EOT Visit should be performed as soon as possible after decision of withdrawal.

²Only SAEs will be assessed.

³ The patient shall stay at hospital for at least 2 hours after the infusion and may be requested to stay longer at the discretion of the investigator.

⁴ The specified visit windows are in accordance with the previous visit. Visit 1 of Cycle 2 and onwards should be performed 7 days ± 3 days after Day 15 of the previous cycle.

⁵ Informed consent must be obtained before or at the Screening Visit window i.e., may be reasonably prior to the screening date.

⁶ Signs and symptoms occurring between Visit 0 and first infusion should be recorded as medical history (see Section 10 for details). SAEs should be reported as of the signing of the informed consent.

⁷ Height is only assessed at the Screening Visit. During the trial, only body weight is measured on the first dosing day in a cycle, as part of the dose calculation. If body weight is assessed \leq 7days before the first day of the planned dosing in a cycle, this value can be used to calculate dose.

⁸ Temperature, blood pressure and heart rate. Within each visit, preferably the same equipment shall be used for vital signs measurements. Vital signs should be assessed just before and no longer than 30 minutes before infusion start, during and after the infusions until 2 hours after end of infusions, as indicated in Section 10.5.

⁹ Optional.

Footnotes to Trial Flowchart: Cohort Expansion Part

¹⁰ One ECG will be performed at screening. Three ECGs should be performed at least 2 minutes apart before infusion of the trial drug on Visit 1 for all cycles, in accordance with the ECG Specifications Manual.

Within 4 weeks prior to Visit C1-V1. All patients will have a CT-scan with contrast of thorax, abdomen and pelvis performed as part of the screening procedure. If a CT-scan has been performed within 4 weeks prior to Visit C1-V1 as part of standard procedure, it is acceptable as screening CT-scan for the trial. If there is suggestion of brain metastases/tumors, a CT-scan of the head will be performed before inclusion.

¹² At the end of every second cycle, i.e., on Day 1 of Cycles 3, 5, 7 and 9, CT-scans can be performed up to 7 days before Day 1 of the relevant cycle to ensure result to be available before subsequent dosing. Additional scan at the EOT Visit. To be completed as indicated to confirm response, new symptoms, end of trial or physician discretion.

¹³ Patients experiencing ocular symptoms must be referred to an ophthalmologist for prompt review (preferably within 72 hours and no later than within one week).

¹⁴ Radionuclide bone scan and PSA will be performed for CRPC patients. Radionuclide bone scan will be performed at screening, every 16 weeks (i.e., Day 1 of Cycles 5 and 9), and upon clinical indication. If there is suspicion of progression, another bone scan will be performed 12 weeks later. The screening radionuclide bone scan can be performed up to 4 weeks prior to Visit C1-V1.

¹⁵ Laboratory parameters will be analyzed centrally.

¹⁶ For patients with ovarian and endometrial cancer.

¹⁷ Flow cytometry only on Cycle 1 and Cycle 5.

¹⁸ HBsAg, anti-HBs and anti-HBc, Hepatitis C and antibodies to CMV antigen will be assessed at screening for all patients; for CMV, anti-IgG and IgM will be assessed and, in case of positive IgM, it will be confirmed with CMV PCR; for HCV, anti-IgG will be assessed and, if positive, it will be confirmed with HCV PCR. HPV only for patients with cervical cancer. At EOT, only antibodies to CMV antigen will be assessed.

¹⁹ See Table 4 and Section 10.17 for details of PK samplings.

²⁰ Archived biopsy material can be forwarded if a sample is available. If no sample is available, a new tumor biopsy must be obtained at least 2 weeks before dosing to ensure healing of wound.

²¹ Only on Cycle 4.

²² Preventive eye therapy to be administered in relation to infusions as detailed in Section 8.4.5.3.

Table 6: PK Sampling - Cohort Expansion Part - After Urgent Safety Measure

Treatment Cycle	Screening		Cycle 1			Cycle 2-9		Unscheduled
Visit Number	0	1	2	3	1	2	3	1-X
Day/Week	-	1d	8d	15d	1d	8d	15d	
Before Infusion (on infusion days)	X	X	X	X	X	X	X	X^2
End of infusion (+15 minutes) ¹		X			X			
+ 2 hours (± 15 minutes) after end of infusion ¹		X						

¹ Allowed time windows are indicated in parentheses.

² Optional.

Final 5.0 (incorporating Protocol Amendment 4) 06 Jul 2017

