7.2.2 Secondary Endpoints

- Safety laboratory parameters (hematology, biochemistry, coagulation factors and flow cytometry)
- Skin disorders
- Bleeding events
- Neuropathy
- PK parameters (clearance, volume of distribution and AUC [AUC0-Clast and AUC0-∞], Cmax, time of Cmax [Tmax], pre-dose values, and half-life of tisotumab vedotin (HuMax-TF-ADC) and free toxin [MMAE])
- Immunogenicity of tisotumab vedotin (HuMax-TF-ADC) (human anti-human antibodies)
- Anti-tumor activity measured by tumor shrinkage (based on CT-scan evaluations), change in PSA and CA 125
- Objective Response (Complete Response [CR] or PR), Disease Control (CR, PR or SD), Progression-Free Survival (PFS) and Duration of Response (DoR)

Final 5.0 (incorporating Protocol Amendment 4) 06 Jul 2017

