Patients in the Cohort Expansion part will be treated with the RP2D from the Dose Escalation part. Patients may receive up to nine cycles of treatment. Reduced dose can be administered in accordance with the mitigation strategies (Section 8.4.4 to 8.4.5.6) or at the discretion of the treating physician based on individual patient observed toxicity profile and quality of life evaluation, and after consultation and agreement by the sponsor Medical Officer.

The specific indications for the Cohort Expansion part will be decided once the RP2D has been determined. Then, inclusion and exclusion criteria for a reduced number of previous lines of treatment will be specified for all potential indications.

[figure not shown]
At the end of the trial, Genmab will ensure provision of continued treatment to patients with clinical benefit defined as SD or better, until unacceptable toxicity or PD is observed. This will be done through a separate extension trial protocol.

Patients will be treated with up to nine cycles. The treatment period will last for up to 36 weeks (or less after changing to the once q3wk dosing scheme) or until unacceptable toxicity or disease progression at the discretion of the treating physician. The treatment duration is shortened compared to the Dose Escalation part in order to align with the treatment duration in the GEN701 trial and since patients with clinical benefit will be ensured continued treatment beyond this duration if so desired.

Severe ocular toxicity has been observed in the dose dense program 1.2 mg/kg 3q4wk and an urgent safety Protocol Amendment 4.0 has been implemented. No patients will further receive the dosing schedule 3q4wk; instead, tisotumab vedotin (HuMax-TF-ADC) 2.0 mg/kg will be administrated once q3wk on Day 1 of each 21-day cycle regardless of the prior dose(s) administered. The next dose of tisotumab vedotin cannot be administered until at least 21 days have elapsed since the last administration.

Figure 4: Dose Scheme for the Cohort Expansion Part After Urgent Safety Measurepresents the new dosing scheme according to the implementation of the urgent safety measure (Protocol Amendment 4.0):

Figure 4: Dose Scheme for the Cohort Expansion Part After Urgent Safety Measure

CE=Cohort Expansion

Nine cycles are expected to correspond to approximately 27 weeks.

Final 5.0 (incorporating Protocol Amendment 4) 06 Jul 2017

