8.1.1.4 Follow-up Phase

Dose Escalation Part

Patients will attend four follow up visits (FU1 to FU4) at six weekly intervals (± 7 days).

If the patient withdraws from treatment and has not started new anti-cancer treatment, or if the patient completes all treatment cycles, the patient will be followed by the site every six weeks for a maximum of four visits or until other treatment is initiated, for a maximum of 24 weeks. Then, the patient will return for an End of Trial (EOT) Visit.

Cohort Expansion Part

No follow-up visits will be included in the Cohort Expansion part.

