8.4.1 Treatments Administered

The investigator must ensure that the trial drug will be used only in accordance with the protocol.

Tisotumab vedotin (HuMax-TF-ADC) will be administered as an intravenous infusion on Days 1, 8 and 15 of each cycle (one treatment cycle is 28 days).

After implementation of the urgent safety measure (Protocol Amendment 4), tisotumab vedotin (HuMax-TF-ADC) 2.0 mg/kg will be administrated once q3wk on Day 1 (one treatment cycle is 21 days), regardless of the prior dose(s) administered. The next dose of tisotumab vedotin (HuMax-TF-ADC) cannot be administered until at least 21 days have elapsed since the last administration.

Each patient's dose will be calculated based on the patient's weight rounded to the nearest kilogram, i.e., assigned cohort dose in mg/kg × body weight in kg. The weight used per cycle should be the weight taken in connection with the first dosing visit of the current cycle (see Section 10.3). For patients whose body mass index (BMI) is greater than 30 kg/m², the investigator should use a weight that, based on the patient's height, corresponds to a maximum BMI of 30.

The dose is calculated according to the following formula if BMI is greater than 30kg/m²:

Dose
$$(mg) = x (mg/kg) * 30 (kg/m2) * height (m) * height (m)$$

Final 5.0 (incorporating Protocol Amendment 4) 06 Jul 2017

Tisotumab vedotin (HuMax-TF-ADC) will be administered over a minimum of 30 minutes. If infusion-related events emerge, refer to Section 8.4.4. The infusion is complete when the infusion line has been flushed with a minimum 15 mL saline. Preventive eye therapy should be administered in relation to infusions as detailed in Section 8.4.5.3.

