9.2.5 Cohort Expansion Part: Safety Follow-up Visit

Patients who withdraw from the trial will return for a Safety Follow-up Visit, 30 days after the last dose of IMP. In the Safety Follow-up Visit, only SAEs will be assessed.

Final 5.0 (incorporating Protocol Amendment 4) 06 Jul 2017

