12.5.5 Host Immune Response

Titers of tisotumab vedotin (HuMax-TF-ADC) will be listed and positive/negative host immune response to tisotumab vedotin (HuMax-TF-ADC) will be summarized (positive/negative). The association between positive/non-positive ADA and PK (pre-dose values and C_{max}), major safety signals (CTCAE grade \geq 3) and efficacy information (change in tumor size by CT-scan) will be explored.

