12.7 Subgroups and Center Effects

Subgroup analyses for the following factors are planned:

- Indication type
- TF expression
- ADA positivity (only for grade \geq 3 AEs and tumor shrinkage endpoints)

Other sub-group analyses may be performed post-hoc. Due to the low number of patients per center no investigation of center effects are planned.

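### In the current Cohort Expansion schedule no scheduled ADA sample is guaranteed after the last dose, and patients who leave before Cycle 2 Day 1 have no scheduled sample that could show treatment-emergent ADA

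*Protocol*

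**What the plan says.** Immunogenicity is a named secondary endpoint in Section 7.2.2: "Immunogenicity of tisotumab vedotin (HuMax-TF-ADC) (human anti-human antibodies)". Section 12.5.5 states that "positive/negative host immune response to tisotumab vedotin (HuMax-TF-ADC) will be summarized (positive/negative)", and that ADA status will be explored against PK, grade ≥3 events and change in tumour size. Section 12.7 lists "ADA positivity (only for grade" ≥3 AEs and tumour shrinkage among the planned subgroup factors.

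Sampling times come only from the flow charts, because Section 10.16.7 on immunogenicity gives none. In Table 5, the schedule in force after Protocol Amendment 4, the row "ADA (Immunogenicity)" is marked at Screening, Cycle 1 Day 1, Day 1 of Cycles 2 to 9, and Unscheduled. It is blank at Day 8, Day 15, EOT and Safety Follow-up.

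Two further statements remove the other places where a late sample could fall. Section 8.1.1.4: "No follow-up visits will be included in the Cohort Expansion part". Section 9.2.5: "In the Safety Follow-up Visit, only SAEs will be assessed".

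On dosing, Section 8.4.1 has "2.0 mg/kg will be administrated once q3wk on Day 1 (one treatment cycle is 21 days)", and Section 8.1 adds "Nine cycles are expected to correspond to approximately 27 weeks".

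**The concern.** Sampling and dosing fall on the same day of the cycle, so the sample that covers a given dose is the one on Day 1 of the next cycle. When there is no next cycle, there is no scheduled sample. This affects two groups: patients who have had their last dose, whenever that is, and patients who leave during Cycle 1, for whom the last dose is also the first.

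The second group matters more. Some events that end treatment, such as anaphylaxis (Section 8.4.4) or a first grade ≥3 keratitis (Section 8.3.4.1), can occur in Cycle 1. Severe events are also what ADA status is to be compared with. Patients with an early severe event are thus among those most likely to have no informative ADA result. Section 8.3.4.5 states that no patient is replaced after Amendment 4, so they are not made up.

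The SAP is not at hand, but it could not repair this: it can choose a denominator, but it cannot recover a sample that was not drawn.

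**Working it through.** The plan states no figure to reproduce. The check is a reading of the schedule followed by a count.

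**Step 1: schedules side by side.** The ADA row of each flow chart was matched cell by cell to its column headings (20 cells in Table 1, 13 in Table 3, 10 in Table 5; all match).

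| Flow chart | Scheduled ADA samples | Follow-up visits | EOT | Safety Follow-up |
|---|---|---|---|---|
| Table 1, Dose Escalation | Screening, Day 1 of each cycle | marked | blank | blank |
| Table 3, Cohort Expansion, superseded | Screening, Day 1 of each cycle | none held | blank | blank |
| Table 5, Cohort Expansion, current | Screening, Day 1 of each cycle | none held | blank | blank |

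All three also mark an unscheduled sample. In Table 5 that cell carries footnote 10, which is the ECG note; the note meaning optional is footnote 9.

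The Cohort Expansion part dropped the follow-up visits, which in Dose Escalation carry the only scheduled ADA samples after treatment, and put nothing at EOT in their place.

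**Step 2: doses followed by a later scheduled on-cycle sample.** Under Table 5 a patient dosed in k cycles receives k doses. The sample on Day 1 of cycle j+1 covers dose j, so k−1 doses are covered.

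- k = 1: 0 of 1
- k = 2: 1 of 2
- k = 4: 3 of 4
- k = 9: 8 of 9

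For nine cycles the last sample and the last dose both fall on study day 21 × (9−1) + 1 = 169. The ninth cycle ends on day 9 × 21 = 189, which agrees with the stated 27 weeks (27 × 7 = 189). No scheduled sample falls in that final interval.

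Under the superseded Table 3, with three doses per cycle, 3(k−1) of 3k doses are covered: 0 of 3 for one cycle and 24 of 27 for nine. The last sample is on day 28 × 8 + 1 = 225 and the last dose on day 28 × 8 + 15 = 239, which is 14 days later.

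**Step 3: what this could do to the incidence (illustration only).** Let p be the true treatment-emergent ADA rate, q the share leaving before Cycle 2 Day 1, and s the share of converters who convert only after their last Day 1 sample. None is given in the protocol. The ranges assumed here are q = 5–20% and s = 0–25%.

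- All exposed patients as denominator: observed rate = p(1−q)(1−s). With p = 10%, this runs from 0.10 × 0.80 × 0.75 = 6.0% to 0.10 × 0.95 × 1 = 9.5%.
- Patients with a post-dose sample as denominator: observed rate = p(1−s). With p = 10%, this runs from 0.10 × 0.75 = 7.5% to 10%.

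The direction follows from the schedule: converters after the last sample can only be missed. The amount depends on the assumptions. The part due to Cycle 1 leavers also depends on whether they are counted as negative or left out. Section 12.2 uses all exposed patients for every endpoint, and Section 12.3.1 counts patients with recorded values. A patient with only baseline ADA values could meet both.

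**The case against.** A reader might infer more than the protocol supports.

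- *That no Cohort Expansion patient is ever sampled after the last dose.* This does not follow. The unscheduled ADA cell is marked, and Section 9.2.3 lets the investigator add assessments. A patient may also attend a Day 1 visit, be sampled and not be dosed, for example because a scan shows progression or dosing is held. That patient has a sample at least 21 days after the last dose. How often this happens cannot be told.
- *That Cycle 1 leavers cannot be ADA positive.* Pre-existing antibodies can be found in their Screening and Day 1 samples. Only treatment-emergent ADA without an unscheduled draw is missed.
- *That every on-treatment sample is taken under full exposure.* Samples from Cycle 2 onward fall at the end of a dosing interval of at least 21 days, if drawn before infusion. The protocol does not state their timing relative to infusion.
- *That a given number of patients is lost, or that the bias has a known size.* No Cycle 1 drop-out rate is given. The first scheduled on-treatment CT is at Cycle 3 Day 1, so progression found on a scheduled scan comes after the Cycle 2 sample.

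Other objections carry some weight. Table 1 also has no ADA at EOT, so Dose Escalation patients who leave before Follow-up Visit 1 share the gap. The two parts are reported separately (Section 12.3), so their different windows are not pooled. The endpoint is descriptive and no formal test depends on it. Finally, EOT in this part has no fixed day and is held promptly once withdrawal is decided, so an EOT sample may come too early to show the response to the last dose.

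These points limit the wording and the weight. They leave the gap itself, because a discretionary sample or an undosed Day 1 visit is not a scheduled sample after the last dose.

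**Conclusion.** The point holds for scheduled samples. Under Table 5 a scheduled ADA sample after the last dose is not guaranteed: k−1 of k doses are followed by an on-cycle sample. A patient who leaves before Cycle 2 Day 1 has none that could show treatment-emergent ADA. Patients who reach Cycle 2 are sampled about 21 days after each earlier dose, so the gap is confined to the last dose and to Cycle 1 leavers.

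Treatment-emergent incidence may be understated, and the ADA comparisons with grade ≥3 AEs and tumour shrinkage may lose early leavers selectively. The size is unknown: the percentages in the illustration rest wholly on assumed rates. The consequence is limited to a descriptive secondary endpoint and exploratory comparisons in 20 to 30 patients. A correction is still worth making because it costs little and the missing information cannot be recovered later.

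**What to change.** 1. Mark ADA at the EOT Visit in Table 5, and state that the sample is due in patients who complete all cycles as well as in those who withdraw. Section 8.1.1.5 describes the Cohort Expansion EOT Visit only for progression, new treatment or withdrawal.
2. Record the days from last dose to that sample, so that early and late EOT results can be told apart.
3. Report treatment-emergent ADA among patients with at least one post-dose sample, and give the number of exposed patients without one.
4. Correct the footnote marker on the unscheduled ADA cell.

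With the EOT sample taken, every dose is followed by a scheduled sample: 9 of 9 instead of 8 of 9 over nine cycles, and 1 of 1 instead of 0 of 1 for a Cycle 1 leaver.

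The cost is one extra tube at a visit that already draws blood for hematology, biochemistry, coagulation and flow cytometry, plus slightly more work in the central ADA batches. No visit is added. The drawback is that some EOT samples, mainly from patients who stop soon after a dose, will be too early to be informative. A negative result from them should not be read as absence of a response.
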